#### Table 5-2Imputation of end dates (AE, CM)

Missing Element	Rule (*=last treatment date plus <30> days not > (death date, cut-off date, withdrawal of consent date))
day, month, and year	Completely missing end dates (incl. ongoing events) will be imputed by the end date of the on-treatment period*
day, month	If partial end date contains year only, set end date = earliest of 31DecYYYY or end date of the on-treatment period *
day	If partial end date contains month and year, set end date = earliest of last day of the month or end date of the on-treatment period*

Any AEs and ConMeds with partial/missing dates will be displayed as such in the data listings. Any AEs and ConMeds which are continuing as per data cut-off will be shown as 'ongoing' rather than the end date provided.

# 5.1.3 **Prior and Concomitant Medication Date Imputation**

The imputation of the start date of concomitant medication will follow the same conventions as for AE start date.

# 5.1.4 Incomplete Date of Diagnosis of Hemochromatosis History

Incomplete dates for date of diagnosis will be imputed with the earliest possible date, provided that at least the year of diagnosis is known, and that imputed diagnosis date occurred before screening visit 1.

# 5.2 Laboratory Parameters Derivations

# 5.2.1 Re-derived Creatinine Clearance

The re-derived creatinine clearance will be calculated using the Cockcroft-Gault equation.

In the formulae below, CrCl denotes Creatinine Clearance in mL/min, SCr denotes Serum Creatinine in  $\mu$ mol/L; age in years is calculated from date of birth and date of the relevant blood sample. Weight and height are the last available measurements at the time of the relevant blood sample.

Cockcroft-Gault formula (≥18 years of age),

CrCl (mL/min)= Male subjects: (140-age (years)) ×weight (kg)/(815×0.001×SCr (µmol/L)) Female subjects: (140-age (years)) ×weight (kg)×0.85/(815×0.001×SCr(µmol/L))

# 5.2.2 Multiple Assessments Within Post-Baseline Visits

All scheduled/unscheduled assessments should be assigned to time windows. In case of multiple values per window, the one closest to the planned visit date should be used. If 2 values are equidistant to the planned visit date, the selection should be made by selecting the one assessed by central (if any) and otherwise - for multiple central assessments equidistant to the planned visit - the last value. When multiple values are reported on the same day then the average value is used in analyses.

For worst post-baseline assessment, all on-treatment values are considered regardless of time windows. All unscheduled and repeat measurements will be included in listings.

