6.1.1 Dosing regimen

Study treatments	Pharmaceutical form and route of administration	Dose	Frequency and/or Regimen
Deferasirox FCT	Tablet for oral use	7 mg/kg (Initial dose)	Daily
Phlebotomy	Venipuncture	NA	determined by PI

Table 6-1 Dose and treatment schedule

After a 4-week screening period, eligible patients will be randomized 2:1 to receive deferasirox FCT or phlebotomy.

Patients randomized to deferasirox FCT will receive 7 mg/kg once daily. The daily dose is calculated based on the patient's weight, then rounded up or down to the nearest whole tablet according to the available strengths of deferasirox FCT tablets (90 mg, 180 mg, and 360 mg; see Appendix 14.1). After 3 months (12 weeks), adjust dose as needed based on SF levels listed below with the maximum dose adjustment of 3.5 mg/kg/day per month.

- SF < $300 \mu g/L$ Decrease to 3.5 mg/kg/day
- SF 300-1000 µg/L Maintain 7 mg/kg/day
- SF > 1000-2000 μ g/L Increase to 10.5 mg/kg/day
- SF > 2000 μ g/L Increase to 14 mg/kg/day

When SF reaches the study target $\leq 100 \ \mu g/L$, deferasirox FCT must be interrupted and the patient enters the maintenance phase.

During the maintenance phase, when SF \geq 300 µg/L, deferasirox FCT 3.5 mg/kg/day may be re-initiated. If deferasirox FCT 3.5 mg/kg/day is not controlling SF and it continues to increase, increase to a maximum 7 mg/kg/day. Treat until the SF reaches \leq 100 µg/L, then interrupt treatment again.

During regular study visits, the investigator or pharmacist will dispense the appropriate number of deferasirox FCT tablets to each patient. The number of tablets of each strength dispensed will be recorded in the study Drug Dosing Log. Each time deferasirox FCT is dispensed, the investigator must provide detailed instructions to patients, instruct them to take the assigned amount of study drug, and return all unused study medication every 4 weeks. Returned study medication must be counted and recorded. The field monitor must note the drug accountability during site visits and at the completion of the trial.

Medication labels must be in the local language and comply with the legal requirements of the countries where the study is implemented. Labels will have study identifier and storage conditions for the study drug, but no patient information.

Patients should swallow the required number of deferasirox FCT, with or without a light meal, and around the same time each day.

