7.1 Study flow and visit schedule

Table 7-1 lists all assessments and indicates with an "X" the visits when they are performed. All data obtained from these assessments must be supported in the patient's source documentation.

Scheduled assessments should be done on the designated day, or as close to it as possible, i.e., not exceeding ± 3 days for assessments scheduled at Week 2 and Week 4, not exceeding ± 7 days for monthly visits until Week 104 (End of Treatment Visit), and not exceeding ± 30 days for assessments done approximately every 6 months, such as ocular and ECG assessments. In this clinical trial, a week is 7 calendar days, and 1 month is 30 days.

FRANCE SPECIFIC ONLY: The additional assessments of creatinine and creatinine clearance at Week 1 and Week 3 after start of treatment, and weekly checks of creatinine and creatinine clearance during the first month of dose increases, are specific to patients enrolled in sites from France. These assessments are NOT included in the Table 7-1, and should be recorded as unscheduled visits.

No eCRF will be used as a source document.

	Category	Protocol Section	Screening		Randomization								Treatment Period					End of study treatment (EoT)	30-day Follow up	Post-treatment Follow-up *
Weeks			-4	-2	Day 1	2	4	8	12	16	20	24	28, 32, 36, 40, 44, 48	52	56, 60, 64, 68, 72	76	80, 84, 88, 92, 96, 100	104	108	
Informed Consent	D	7.1.2	Х																	
IRT Registration	S	7.1.2.1	Х																	
Demography	D	7.1.2.3	Х																	
Inclusion/ exclusion	D	7.1.2	Х	Х																
HH history	D	7.1.2	х																	
Medical History	D	7.1.2.3	Х																	
Prior and concomitant medication / procedures	D	6.4	Con	tinuou	ısly till 30	day	s aft	er las	st dos	se of	study	treatr	nent							
Ocular History	D	7.1.2.3	Х																	

Table 7-1 Visit evaluation schedule

Novartis Amended Protocol Version 01 (Clean)

	Category	Protocol Section	Screening		Randomization								Treatment Period					End of study treatment (EoT)	30-day Follow up	Post-treatment Follow-up *
Weeks			-4	-2	Day 1	2	4	8	12	16	20	24	28, 32, 36, 40, 44, 48	52	56, 60, 64, 68, 72	76	80, 84, 88, 92, 96, 100	104	108	
Cirrhosis History	D	7.1.2	Х																	
Randomization	D	6.5			х															
Disposition	D	7.1.2		X														Х		Х
Molecular Testing of HH	D	7.2.2.6.1	X																	
Physical examination	S	7.2.2.1	Х		x	х	Х	х	Х	Х	х	Х	x	х	Х	Х	Х	Х		
Vital signs	D	7.2.2.2	Х		Х	Х	Х	Х	Х	Х	х	Х	Х	Х	Х	х	х	Х		

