7.1.4 Treatment period

The study treatment duration is 24 months (104 weeks). Patient visits will occur bi-weekly for the first 4 weeks, then every 4 weeks from Week 4 until 104 (EOT).

All visits should be scheduled respective to the randomization date (Day 1), rather than in relation to previous visits.

After completing screening, eligible patients will be enrolled and randomized to receive phlebotomy or deferasirox FCT. For deferasirox FCT, the target daily dose is calculated by the physician based on the patient's actual body weight.

At the start of treatment, patients randomized to deferasirox FCT will receive 7 mg/kg once daily. Patient randomized to phlebotomy may receive treatment at a frequency determined by the treating physician.

For details on study design and dose adjustments, see Section 4 and Section 6.3.

For details on assessments during the treatment period, see Table 7-1.

FRANCE SPECIFIC ONLY: The additional assessments of creatinine and creatinine clearance at Week 1 and Week 3 after start of treatment, and weekly checks of creatinine and creatinine clearance during the first month of dose increases, both specific to patients enrolled

in sites from France only, are NOT included in the Table 7-1, and should be regarded as unscheduled visits.

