7.2.2.6.3 Clinical chemistry

Clinical chemistry samples will be collected at Screening and at subsequent time points as specified in Table 7-1.

Clinical chemistry parameters assessed are listed in Table 7-3.

In accordance with the deferasirox label, serum creatinine, creatinine clearance, alkaline phosphatase, ALT/SGPT, AST/SGOT, direct (conjugated) bilirubin, indirect bilirubin, total bilirubin must be assessed in duplicate before the initiation of therapy to establish a reliable pre-treatment baseline.

FRANCE SPECIFIC ONLY: Serum creatinine and creatinine clearance should be assessed at weeks 2 and 4 after initiation of deferasirox FCT as central lab tests. For patients enrolled in sites in France, serum creatinine and creatinine clearance will also be assessed at weeks 1 and 3 after initiation of deferasirox FCT, and weekly during the first month after dose increases. The assessment is to be performed by the central lab however the local lab may be used. In the clinical database, "Unplanned Central Lab Cover Page" should be used to enter these unscheduled samples information at 'Unplanned' visit, or "Biochemistry Local Unplanned page" will be used in case of local lab assessment. The CRA will obtain the local laboratory reference ranges and a copy of the laboratory certification

Creatinine clearance will be calculated using the Cockcroft-Gault formula every time serum creatinine is collected.

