#### 2.6.7 Laboratory Data

On analyzing laboratory, data from all sources (central and local laboratories) will be combined. The summaries will include all assessments available for the lab parameter collected no later than 30 days after the last study treatment administration date (see Section 2.1.1).

The following summaries will be produced for hematology, urinary, and biochemistry laboratory data (by laboratory parameter and treatment):

- Descriptive Statistics for lab results and change by from baseline time point and treatment arm
- Shift tables using notable/extended ranges to compare baseline to the worst on-treatment value for key lab parameters (see Table 2-1)
- Shift tables using the low/normal/high/(low and high) classification to compare baseline to the worst on-treatment value.
- Trends of key lab parameter values over time (baseline and selected on-treatment timepoints) will be displayed via boxplots based on time windows and corresponding tables displaying the statistics used for the box plots by the selected time points.

The following listings will be produced for the laboratory data:

- Listings of all laboratory data, with classification relative to the laboratory normal range.
- Listing of all lab abnormalities based on notable/extended ranges

Parameter	Criteria
Absolute neutrophils	$< 1.5 \times 10^{9}$ /L (extended range $< 0.5 \times 10^{9}$ /L)
Platelets	$< 100 \times 10^{9}$ /L (extended range $< 50 \times 10^{9}$ /L)
Hemoglobin	< 100 g/L
ALT and AST	$> 5 \times$ ULN and $> 2 \times$ baseline (extended range $> 10 \times$ ULN and $> 2 \times$ baseline)
Total bilirubin	> 2 x ULN
Serum creatinine	> 33% increase from baseline and > ULN at 2 consecutive measurements at least 7 days apart
Creatinine clearance	< 60 mL/min at 2 consecutive measurements at least 7 days apart (extended range < 40 mL/min at least 7 days apart)
Urinary protein/creatinine ratio*	$\geq$ 1.0 mg/mg at 2 consecutive measurements at least 7 days apart

 Table 2-1 Definition of notable/extended ranges for key safety laboratory parameters

Novartis	Confidential	Page 29 of 36
SAP Amendment 1		Study No. CICL670F2203

\* If the unit of the parameter (Urinary protein/creatinine ratio) is in mg/mmol then will have to use a conversion factor as 0.00885 to convert into mg/mg unit for further derivation.

For all analyses, creatinine clearance will be re-derived using the Cockcroft-Gault equation described in Section 5.2.1.

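### Extra creatinine samples at French sites, unequal between arms, enter the worst-value and confirmed renal tables, and the SAP plans no version at equal planned sampling

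*SAP*

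**What the plan says.** **Sampling.** Under Protocol 7.1.4 and Table 7-1, both arms have chemistry at Weeks 2 and 4 and then every 4 weeks to Week 104. For French sites, Protocol 7.2.2.6.3 sets further checks of creatinine and its clearance: they "will also be assessed at weeks 1 and 3 after initiation of deferasirox FCT, and weekly during the first month after dose increases". Protocol 7.1 says that the additional checks "are specific to patients enrolled in sites from France" and are recorded as unscheduled visits. It speaks of Weeks 1 and 3 after start of treatment and names no arm; 7.1.4 and the description of the French amendment do the same.

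**Analysis.** SAP 2.6.7 combines central and local laboratories and adds: "The summaries will include all assessments available for the lab parameter collected no later than 30 days after the last study treatment administration date". The shift tables compare baseline with the worst on-treatment value, for which SAP 5.2.2 states: "For worst post-baseline assessment, all on-treatment values are considered regardless of time windows". The notable criterion for serum creatinine in SAP Table 2-1 is "> 33% increase from baseline and > ULN at 2 consecutive measurements at least 7 days apart"; creatinine clearance below 60 mL/min is also judged on two consecutive values at least 7 days apart. One value per window applies only to outputs by time point. Centres are pooled with no centre effect (SAP 2.1), the subgroup section is marked not applicable (SAP 2.1.2), and no table restricted to scheduled visits is planned.

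**The concern.** Laboratory abnormalities are part of a secondary endpoint (Protocol Table 3-1, SAP Table 1-1), and Protocol 10.5.3 has safety assessed between the arms partly through them. Renal function is a recognised issue for this drug: Protocol 2.6 reports creatinine rises in the earlier hemochromatosis study.

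If one arm is sampled more often, a worst-value table records more abnormalities there even when the underlying process is the same. A two-value criterion with only a minimum gap of 7 days can also confirm a short rise under weekly sampling that would be seen once, or not at all, under 4-weekly sampling. Part of any deferasirox excess in these tables could then reflect sampling intensity, and the planned outputs give the reader no means of separating the two.

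**Working it through.** The documents give no figure on this point, so there is none to reproduce. The schedule comes from the documents. The abnormal rate per sample, the length of a rise and the French share are assumptions, because the documents give none of them.

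**1. Planned post-baseline samples.** Routine: Week 2 plus Weeks 4, 8, ..., 104 = 1 + 26 = 27. French additions: 2 (Weeks 1 and 3) plus 3 per dose increase, since the fourth weekly check coincides with a routine visit. Protocol 6.1.1 sets a "maximum dose adjustment of 3.5 mg/kg/day per month", so going from 7 to 14 mg/kg/day takes two steps. The totals are 27 + 2 = 29, 29 + 3 = 32 and 32 + 3 = 35, that is +7%, +19% and +30%. Increases in the maintenance phase would add three each and are not counted.

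**2. Worst value.** With abnormal rate p per independent sample, P(at least one abnormal in m samples) = 1 - (1 - p)^m. The last column is French share × (35-sample figure - 27-sample figure), for shares of 10% and 40% with every French patient having two increases.

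| p | 27 | 29 | 32 | 35 | Arm-level rise, 10% to 40% share |
|---|---|---|---|---|---|
| 0.2% | 5.26% | 5.64% | 6.21% | 6.77% | 0.15 to 0.60 points |
| 0.5% | 12.66% | 13.53% | 14.82% | 16.09% | 0.34 to 1.37 points |
| 1% | 23.77% | 25.28% | 27.50% | 29.66% | 0.59 to 2.36 points |
| 2% | 42.04% | 44.34% | 47.61% | 50.69% | 0.86 to 3.46 points |

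At p = 1% with no dose increase, the arm-level rise is 1.51 × 0.1 to 1.51 × 0.4 = 0.15 to 0.60 points. If French phlebotomy patients also have Weeks 1 and 3, and the French share is equal in both arms, the contrast is 35 against 29 samples: 4.37 × 0.1 to 4.37 × 0.4 = 0.44 to 1.75 points.

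**3. A single rise lasting D days.** With exact spacing g and random onset, P(seen) = min(1, D/g) and P(two consecutive samples inside it) = min(1, max(0, D/g - 1)). The comparator is 28-day spacing after a dose increase, but 14-day spacing in the first month, because every patient is sampled at Weeks 2 and 4.

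| D | Confirmed, g = 28 | Confirmed, g = 14 | Confirmed, g = 7 |
|---|---|---|---|
| 10 | 0% | 0% | 43% |
| 14 | 0% | 0% | 100% |
| 21 | 0% | 50% | 100% |
| 28 | 0% | 100% | 100% |
| 42 | 50% | 100% | 100% |

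**4. The confirmed criterion can move either way.** Abnormal values on days 15 and 29 form a confirmed pair. An extra normal value on day 22 removes it. If consecutive means adjacent, abnormal values on days 15, 20 and 26 do not qualify, although days 15 and 26 alone would.

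**5. Net effect on confirmed events.** The same simulated patients (4,000 per scenario) were classified with and without the French samples. Abnormal episodes averaged 10, 30 or 120 days and took up 2%, 2% or 5% of the time; visit days were jittered; 15% of values in an episode and 1.5% outside it were misread. On the adjacent-pair reading:

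| Mean episode | No increase | Two increases |
|---|---|---|
| 10 days | 4.20% to 4.50% | 4.80% to 7.07% |
| 30 days | 10.68% to 10.65% | 10.05% to 11.38% |
| 120 days | 19.05% to 19.12% | 17.70% to 18.12% |

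Across these scenarios 0.10% to 2.45% of patients gained a confirmed event and 0.02% to 0.32% lost one. The largest net change is 7.07 - 4.80 = 2.27 points; at a 40% French share that is 0.4 × 2.27 = 0.91 points for the arm.

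With independent samples instead, P(a run of two) goes from 0.26% (27 samples) to 0.34% (35) at p = 1%, from 6.03% to 7.81% at p = 5%, and from 21.35% to 26.94% at p = 10%. At a 40% share these are rises of 0.03, 0.71 and 2.23 points. The last case is extreme: p = 10% would give 1 - 0.9^27 = 94% of patients at least one abnormal value on the routine schedule.

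**The case against.** Using every on-treatment value is a stated and conservative choice for a safety table, the additional rises may be real, and the analysis is descriptive. Unscheduled values are listed, so a sensitivity table could be made later. All of this is fair, and it is why the all-values tables should stay as the main display. It does not make the two arms comparable at equal planned sampling, and descriptive incidences are still what readers will compare.

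Four stronger readings are tempting, but the documents do not support them:

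- *That confirmed renal events must rise.* Certainty of direction holds only for the single worst value. The confirmed criterion needs consecutive abnormal values, and an extra normal value can break a pair.
- *That the excess will appear as a cluster after start or after a dose increase and look like a dose effect.* The worst-value and notable-range tables cover the whole on-treatment period. Any excess sits in the overall figure.
- *That the Week 1 and 3 samples are settled as deferasirox-only.* Protocol 7.2.2.6.3 says so; 7.1 and 7.1.4 name no arm. Only the post-increase samples are certain to fall on one arm.
- *That France is the only source of uneven sampling.* Protocol 6.3.3 requires follow-up at least weekly for 4 weeks after an interruption for an adverse event or abnormal laboratory value, in all countries, and Protocol 7.2.2.6 allows medically indicated local tests.

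The size is also open to challenge. Independence of repeated creatinine values in one patient is a simplification. Two increases in every French patient is an upper-end case: in the initial phase the 14 mg/kg/day step is tied to serum ferritin above 2000 µg/L, while entry requires only 500 µg/L.

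**Conclusion.** The point holds in a limited form. French sites add creatinine and clearance samples that are unequal between arms at least after dose increases, the SAP takes them into the worst-value and confirmed tables, and nothing planned shows the comparison at equal planned sampling. For worst value the push on deferasirox incidence can only be upward. For confirmed events the expected net effect is nil or upward.

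The arm-level size is modest: at p = 1%, about 0.6 to 2.4 points for worst value (0.15 to 3.5 points over p = 0.2% to 2%), and up to about 0.9 points for confirmed events in the simulated scenarios. These figures assume a French share of 10% to 40% and two increases in every French patient. They shrink with fewer increases, and shrink further if French phlebotomy patients also have the Week 1 and 3 samples. The documents do not support a claim that these tables will mislead on a large scale.

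**What to change.** 1. In SAP 2.6.7, keep the all-values tables as the main safety display. Add a supplementary version of the creatinine and creatinine-clearance worst-value and notable-range tables restricted to nominal Protocol Table 7-1 visits. This also removes the outcome-driven follow-up samples.
2. Do not use one value per window for this purpose. SAP Table 5-3 puts Week 2 at days 2-11 and Week 4 at days 19-25. Counted as elapsed weeks from Day 1, the French Week 1 and 3 samples fall on days 8 and 22, inside those windows, while routine Weeks 2 and 4 fall on days 15 and 29, outside them.
3. Report the number of creatinine samples per patient by arm, and state how consecutive treats samples less than 7 days apart.
4. Reconcile Protocol 7.1, 7.1.4 and 7.2.2.6.3 on which arm has the Week 1 and 3 samples.

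The cost is SAP wording, one repeated set of renal tables and one count. The supplementary version misses rises seen only at extra visits, and after Week 4 its confirmation interval is in effect about 28 days; the main tables and listings still show every event.

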# 5.3 Time-Windows

# 5.3.1 Safety Laboratory Assessments

Safety laboratory data (biochemistry, hematology, and urinary parameters as well as serum creatinine, creatinine clearance and proteinuria) will be collected at screening visits, at each regularly subject visit and at end of treatment visit.

Novartis	Confidential	Page 34 of 36
SAP Amendment 1		Study No. CICL670F2203

If two or more assessments are performed within a time window, then the assessment closest to the planned visit is used in analyses by time window. When two values are equidistant from the planned assessment, the later one is used in analyses. When multiple values are reported on the same day then the average value is used in analyses. For parameters with categorical results, the one from central laboratory is used in analyses.

Table 5-3 shows the defined time windows.

Time Window	Planned Visit Timing	Time Window Definition	
On treatment			
Baseline	On or before Study Day 1*	≤ Study Day 1	
Week 2	Study Day* 8	Study Days 2 – 11 (excluded baseline assessment)	
Week 4	Study Day* 22	Study Days 19 – 25	
Every 4 weeks thereafter			
Week $y=4+(4*k)$	Study Day (4+4*k-1)*7+1	Study Days	
(with $k = 1, 2, 3, 4, 5, 6, 7, 8, 9$ ,		(5+4*k-1)*7+1-14 to	
10, 11,,25)		(5+4*k-1)*7+1+13	
End of treatment	NA	Data collected at EOT visit are included if obtained within the next 30 days of last non-0 dose for DFX intake / non 0 volume removed for Phlebotomy	

Table 5-3 Time windows for safety laboratory data

\*Study Day 1 = first day of study treatment

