7.2.2.5 Ocular examination

Ophthalmologic examinations must be conducted approximately every 6 months for at least 5 ocular assessments at screening and Weeks 24, 52, 76, and 104 (EOT).

An exception is for patients eligible for the Post-treatment Ocular Follow-up phase and EOT occurs in the interval between the scheduled 6-month exams (the allowed assessment window is 30 days +/- of the scheduled date), an ophthalmologic exam is part of the EOT then they will continue their regular schedule of ophthalmological exams every 6 months (recorded in Post-treatment follow-up eCRFs at Weeks 52, 76 and 104 as appropriate) for a total of 6 ocular examinations. A reminder by the site at least one month prior to each upcoming ophthalmological visit should be made. To provide consistent assessments, it is recommended that ocular assessments be performed at the same site with the same equipment for each patient.

The ophthalmologic examination includes the following assessments:

- Best corrected visual acuity must be done using Early Treatment Diabetic Retinopathy Study (ETDRS)
- Slit lamp examination: any opacity graded using the Lens Opacities Classification System, version III (LOCS III)
- Intraocular pressure (IOP) measured by tonometry should be performed after the above two ocular tests
- Dilated fundus exam and color fundus photography

The dilated fundus exam must assess the vitreous, retina, macula, and optic nerve for both eyes. Wide-angle fundus photography of the retina and optic nerve is preferred; however, if unavailable, a regular camera capturing 7 standard stereoscopic fields is allowed.

Detailed instructions for the ophthalmic assessments are provided in the "Manual of Ophthalmic Procedures".

 Table 7-2
 Central imaging assessments collection plan

	00	•
Procedure	Baseline	During Treatment
Color Fundus Photography	Required	Every 6 months (Screening and weeks 24, 52, 76, and 104)

The ocular examination will be performed by a local, qualified ophthalmologist and the results will be documented on the eCRF page. The color fundus photography will not be reported locally and instead be sent to an imaging Contract Research Organization (CRO) designated by Novartis for reading.

Novartis	
Amended Protocol Version 01 (Clean)	

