#### **Study Day**

The study day **for safety assessments** (e.g. adverse event onset, laboratory abnormality occurrence, vital sign measurement, Electrocardiogram (ECG), Ocular, etc.) will be calculated using the start date of study treatment as the reference. For assessments occurring

- On or after the start date of study treatment, the study day will be calculated as (date of safety assessment) (start date of study treatment) + 1. Study day 1 will therefore be the first day of study treatment.
- **Before the start date of study treatment**, the study day will be calculated as (date of safety assessment) (start date of study treatment).

For example, if an adverse event starts 3 days before the start of study treatment the study day displayed on the listing will be negative, i.e. -3.

The study day **for efficacy assessments** (i.e. serum ferritin) will be calculated using the randomization date as the reference. For assessments occurring

- On or after randomization date, the study day will be calculated as (date of non-safety assessment) (date of randomization) + 1. Then study day 1 will be the day of randomization.
- **Before randomization date**, the study day will be calculated as (date of non-safety assessment) (date of randomization).

The study day will be displayed in the data listings.

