#### Baseline

Baseline is considered as the result of an investigation describing the 'true' uninfluenced state of the subject.

For **efficacy evaluations**, (e.g. serum ferritin), the last available assessment before or on the date of randomization is taken as 'baseline' value or 'baseline' assessment.

For **safety evaluations** (e.g. laboratory, vital signs, ocular etc.) the last available assessment before or on the date of start of study treatment is taken as 'baseline' value or 'baseline' assessment.

If subjects have no value as defined above, the baseline result will be missing.

If an assessment is planned to be performed prior to the first administration of study treatment in the protocol and the assessment is performed on the same day as the first administration of study treatment, it will be assumed that it was performed prior to study treatment administration if assessment timepoint is not collected or is missing. Unscheduled assessments will be considered in the determination of baseline.

Subjects who start treatment and discontinue from the study on the same day may have 2 different sets of data collected on study Day 1, one being reported to the Day 1 visit, the other reported to the EOT visit. Data reported at the EOT visit are not eligible for baseline selection.

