#### 5.3.2 Ocular Assessments

Ocular data will be collected at screening visit, at week 24, 52, 76, 104 (EOT) visits. If two or more assessments performed within a time window, then the assessment closest to the planned visit is used in analyses by time window. When two values are equidistant from the planned assessment, the later one is used in analyses. The windowing defined is applicable for both on-treatment & post-treatment time periods. For the summaries by time point, we will be presenting the time points as defined below (Table 5-3).

For worst post-baseline assessment, all on-treatment values and post treatment values are considered regardless of time windows.

Table 5-4 shows the defined time windows.

Time point (Weeks)	Study Day	Lower Limit (day)	Upper Limit (day)
Baseline (Screening)	1*	-30	1
Week 24	162	2	259
Week 52	358	260	441
Week 76	526	442	623
Week 104	722	624	819

Table 5-4 Time windows for Ocular data

**End of Treatment -** Data collected at the EOT visit if conducted within 30 days of EOT date on disposition (DS) page in CRF.

For the post-baseline assessments among discontinued subjects, if no data were collected at the EOT visit the last available post-baseline on-treatment data will be used for EOT.

**\*Study Day 1** = first day of study treatment

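### SAP Table 5-3 plans visits one week early, so for same-day starts its Week 2 and Week 4 windows contain no visit day that the protocol permits

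*SAP*

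**What the plan says.** **Protocol.** Section 7.1.4 fixes the visit clock: "All visits should be scheduled respective to the randomization date (Day 1), rather than in relation to previous visits". It places visits two weeks apart up to Week 4 and four weeks apart from there to Week 104. Section 7.1 defines a week as 7 calendar days. It allows a deviation "not exceeding ± 3 days for assessments scheduled at Week 2 and Week 4", 7 days either way for the monthly visits, and 30 days either way for the six-monthly assessments.

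**SAP, study day.** For safety data (Section 2.1.1), study day "will be calculated using the start date of study treatment as the reference".

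**SAP Table 5-3 (Section 5.3.1).**
- Week 2: planned Day 8, window "Study Days 2 – 11 (excluded baseline assessment".
- Week 4: planned Day 22, window Days 19-25.
- Week 4+4k, for k = 1 to 25: planned day (4+4k-1)×7+1, window from (5+4k-1)×7+1-14 to (5+4k-1)×7+1+13.

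SAP Section 5.2.2 requires every assessment, scheduled or not, to be placed in a window, and takes the value nearest the planned day when there are several. SAP Section 2.6.8 sends vital signs to the same table.

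**SAP Table 5-4 (Section 5.3.2, ocular).** Planned Days 162, 358, 526 and 722, with wide adjoining windows and the rule "If two or more assessments performed within a time window, then the assessment closest to the planned visit is used".

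**The concern.** The Week 2 and Week 4 limits look like the protocol's 3-day tolerance placed around a day that is a week too early: 8+3 = 11, and 22±3 gives 19-25. If so, a patient who attends exactly on schedule has no value in either row.

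The outputs at stake are the by-time-point laboratory statistics and changes from baseline (SAP 2.6.7), the laboratory box plots and their tables if Weeks 2 and 4 are among the selected time points, and the by-visit vital-sign changes planned in Protocol 10.5.3.4. The rows would not simply be empty. Protocol 7.2.2.6.3 adds creatinine and creatinine clearance checks at French sites one and three weeks after deferasirox is started. Those samples fall on Study Days 8 and 22, so they would fill the rows labelled Week 2 and Week 4.

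**Working it through.** **1. Reproduce the SAP's planned days.** All of them follow (w-1)×7+1, the first day of the w-th week:
- Table 5-3: Week 2 = 8, Week 4 = 22, Week 8 = 50, ..., Week 104 = 722.
- Table 5-4: Week 24 = 162, Week 52 = 358, Week 76 = 526, Week 104 = 722.

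**2. Protocol visit day.** Week w is w weeks of 7 days after Day 1, so it falls on Day 7w+1. The difference is (7w+1) - [(w-1)×7+1] = 7 days for all 27 post-baseline planned days in Table 5-3 and all 4 in Table 5-4.

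**3. Compare permitted days with windows, treatment starting on the randomization day.**

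| Visit | Protocol day | Permitted | Table 5-3 window | Permitted days inside |
|---|---|---|---|---|
| Week 2 | 15 | 12-18 | 2-11 | 0 of 7 |
| Week 4 | 29 | 26-32 | 19-25 | 0 of 7 |
| Week 8 | 57 | 50-64 | 43-70 | 15 of 15 |
| Week 104 | 729 | 722-736 | 715-742 | 15 of 15 |

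The Week 8 window comes from (5+4-1)×7+1 = 57, then 57-14 = 43 and 57+13 = 70. From Week 8 on, the windows are therefore built around 7w+1 and contain every permitted day.

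**4. Days with no window.** Days 12-18 (7 days) and 26-42 (17 days) are uncovered: 24 of the 41 days from Day 2 to Day 42. This conflicts with SAP 5.2.2.

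**5. Effect of the early planned day from Week 8.** An on-time Week 8 visit on Day 57 is 7 days from planned Day 50. Any extra sample on Days 44-56 is nearer and would be used instead. With planned Day 57, none would displace it. Such extra samples are foreseen: Protocol Table 6-2 calls for weekly liver tests in several of its hepatic interruption cases.

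**6. Ocular windows.** The permitted ranges are 169±30 = 139-199, 365±30 = 335-395, 533±30 = 503-563 and 729±30 = 699-759. They lie wholly inside 2-259, 260-441, 442-623 and 624-819, so 61 of 61 permitted days are captured at each visit. The cut points 260, 442 and 624 are midpoints of the shifted planned days. Midpoints of the corrected days would be 267, 449 and 631, and no permitted exam lies between the two sets.

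**The case against.** **The SAP may use another meaning of week.** Reading Week w as Day 7w reduces the shift to 6 days and saves one edge day per window (Day 11 and Day 25). Reading it as the first day of the w-th week reproduces the planned days, but puts one week between Day 1 and Week 2 and two weeks between Weeks 2 and 4, which is not the protocol's schedule. Neither reading explains why the same table builds its windows around 7w+1 from Week 8, and neither closes the uncovered days.

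**The failure depends on when treatment starts.** This stands, and the claim is limited accordingly. With a 7-day delay from randomization to first treatment, all 7 permitted days would fit each early window. Same-day start is nevertheless the planned case, since SAP 1.1 has both arms beginning on Day 1.

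A reader might go further and infer that late starters, such as a patient with a late first phlebotomy, are mislabelled throughout and that the windows must be counted from randomization. The documents do not support that. The SAP deliberately separates the two clocks: efficacy study day "will be calculated using the randomization date as the reference", while for safety baseline "the last available assessment before or on the date of start of study treatment is taken as" the baseline value. At a 28-day delay, an on-time Week 12 visit (Day 85) is Study Day 85-28 = 57, which is eight weeks after first treatment. The Week 8 row is then correct by the SAP's own definition. The documents give no actual delays.

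**Ocular displacement.** After early discontinuation, Protocol 7.2.2.5 says "an ophthalmologic exam is part of the EOT then they will continue their regular schedule of ophthalmological exams every 6 months". A reader might infer that the early planned day lets an end-of-treatment exam displace a scheduled one. SAP 5.3.2 gives end of treatment its own data rule and does not say that this exam also competes for the scheduled row, so the displacement is not established.

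**Reach.** Only 2 of the 27 laboratory rows fail, and the outputs are descriptive. This limits the consequence. It does not make the rows right.

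**Conclusion.** The error is real and should be fixed. For patients treated from the randomization day, Table 5-3 captures 0 of 7 permitted days at Week 2 and 0 of 7 at Week 4. On-schedule values at those visits are lost from the by-time-point laboratory and vital-sign summaries. The early planned days from Week 8 on, and in Table 5-4, are a minor consistency matter, because those windows hold every permitted visit.

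The conclusion rests on Week w being Day 7w+1, on same-day starts, and on the windows being programmed as written.

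It would be wrong to infer that the main results are at risk. The primary endpoint uses all post-baseline ferritin values to Week 104. Time to response uses actual dates. Ocular adverse event incidence uses the on-treatment period, or the overall period in its repeat. Worst-value tables ignore the windows, and listings include every measurement.

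**What to change.** **Table 5-3.** Set the planned day to 7 × week + 1: Week 2 = Day 15, Week 4 = Day 29, Week 4+4k = Day 28k+29. Make the early windows contiguous, for example Week 2 = Days 2-21 and Week 4 = Days 22-42, which meets the existing Week 8 window at Day 43. Leave the windows from Week 8 on as they are. For same-day starts the French samples on Days 8 and 22 are then each 7 days from the planned day, against at most 3 for a permitted visit, so the scheduled value is selected.

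**Table 5-4.** For consistency, set the planned days to 169, 365, 533 and 729. The limits can stay.

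**Side note.** These windows do not settle late starts. With a 7-day delay, the permitted Week 4 days 26-32 become Study Days 19-25, of which only 22-25 (4 of 7) fall in the suggested Week 4 window. The sponsor should check the actual delays and state whether by-visit rows mean time since first treatment or scheduled visit.

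**Cost.** Correction of two SAP tables and reprogramming of the visit windows. No new data are needed.
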